¹ If needed, cognitive behavioral assessments may be completed over 2 consecutive working days for feasibility and subject comfort. The following efficacy assessments should, whenever possible, be completed in the following order: MCCB, [REDACTED] SCI-PANSS, UPSA-Bi, SCoRS, CGI-S, CGI-I.

² The visit window is ± 3 calendar days relative to baseline. The total time between visits is not to exceed 10 calendar days (for Week 2) or 17 calendar days (for all other visits).

³ Week 12 (Day 85/ET) assessments should be completed in the event of early subject withdrawal/early termination (ET).

⁴ The site will review all Screening Visit assessments against the inclusion/exclusion criteria, assess for any changes from screening, and reconfirm eligibility prior to randomization.

⁵ C-SSRS “Since Last Visit” evaluation.

⁶ The following safety assessments should, whenever possible, be completed in this order: C-SSRS, concomitant medications, weight, physical examination, neurological examination, SARA, 12-lead ECG, vital signs, urine drug and alcohol screening, blood/urine specimens.

⁷ See Section 8.3 and the Study Reference Manual for additional information.

⁸ All women of childbearing potential and all men must practice effective contraception during the study. After their last dose of study treatment, men and women must continue with contraception for at least 30 days.

⁹ To be performed predose for all study sites. For Japanese study sites, see Footnote 10 for additional instructions.

¹⁰ **For Japanese study sites only** (items designated with Footnote 10 are for Japanese sites only unless otherwise specified):

- On Day 1, in addition to baseline assessments, a [REDACTED] will be collected (see Table 5 for timing) and additional safety evaluations (AE recording, 12-lead ECG, brief neurological examination, and SARA) will be performed 2-hours postdose. Should any abnormal findings arise during these evaluations, an additional [REDACTED] will be collected. Dosing will be performed under medical supervision, and observation may be extended at the Investigator’s discretion prior to discharge from the site, if necessary, including an overnight stay.
- On Day 8, a [REDACTED] will be collected (see Table 5 for timing), and additional safety assessments 2-hours postdose (AE recording, 12-lead ECG, brief neurological examination, and SARA) will be performed.

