14.1.6. Electrocardiogram

Triplet and single ECGs will be collected as specified in the Schedules of Activities (Section 5). Samples obtained outside the proposed sampling timepoints specified in will not be captured as a protocol deviation, as long as the exact time of the assessment is noted on the source document and data collection tool (e.g., CRF).

All scheduled ECGs should be performed after the subject has rested quietly for at least 10 minutes in a supine position. Triplet 12-lead ECGs will be obtained approximately 2 to 4 minutes apart; the average of the triplet ECG measurements collected before dosing on Day 1 will serve the subject's baseline QTc value. When the timing of these measurements coincides with a blood collection, the ECG should be obtained prior to the nominal time of the blood collection, blood pressure, and pulse rate.

To ensure safety of the subjects, a qualified individual at the study site will make comparisons to baseline measurements. If the QTc interval is increased by ≥ 45 msec from the baseline, or an absolute QTc value is ≥ 500 msec for any scheduled ECG, then 2 additional ECGs will be collected (approximately 2 to 4 minutes apart) to confirm the original measurement. If either of the QTc values from these repeated ECGs remains above the threshold value (≥ 45 msec above the baseline) or is ≥ 500 msec, then a single ECG must be repeated at least hourly until QTc values from 2 successive ECGs fall below the threshold value that triggered the repeat measurement.

If QTc values are >500 msec (or ≥ 45 msec above the baseline) for more than 4 hours (or sooner at the discretion of the Investigator), or if QTc intervals get progressively longer, the subject should undergo continuous ECG monitoring. A cardiologist should be consulted if QTc intervals do not return to <500 msec (or to <45 msec above the baseline) after 8 hours of monitoring (or sooner at the discretion of the Investigator).

In some cases, it may be appropriate to repeat abnormal ECGs to rule out improper lead placement as contributing to the ECG abnormality. It is important that leads are placed in the same positions each time in order to achieve precise ECG recordings. If a machine-read QTc value is prolonged, as defined above, repeat measurements may not be necessary if a qualified physician's interpretation determines that the QTc values are in the acceptable range.

CONFIDENTIAL

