4. STATISTICAL ANALYSIS METHODS

4.1 General Considerations

This statistical analysis plan (SAP) describes the planned analyses for this phase 2 study evaluating the primary, secondary [REDACTED] objectives. This SAP also covers the planned interim and final analyses, and therefore there is no separate SAP for the interim analysis.

Data listings will be provided by treatment group, visit, and subject, if applicable. Summary statistics and statistical analyses will only be presented for data where detailed in this SAP. For continuous data, summary statistics will include the arithmetic mean, arithmetic standard deviation (SD), median, minimum (Min), maximum (Max) and n; for log-normal data the geometric mean and geometric coefficient of variation (CV) will also be presented. For categorical data, frequency count and percentages will be presented. Data listings will be provided for all subjects up to the point of withdrawal, with any subjects excluded from the relevant population highlighted. Summary statistics and statistical analyses will generally only be performed for subjects included in the relevant analysis population.

Data will be summarized and presented by treatment group, defined in Table 1. Data will be listed by treatment group. Exposure to study medication will be tabulated by treatment group.

Unless stated otherwise, baseline data are defined as the data collected prior to the time and/or on the day of the first dose, which is usually the same day as the Day1/Baseline visit. If data are not available on Day 1 for safety assessment, the measurements recorded up to 3 days prior to first dose (i.e. Day -3) will be used as baseline. For efficacy assessments, the Day1/Baseline visit may be performed over 2 days, i.e., on Day 1 and Day 2. Therefore, an assessment performed on the second day of visit Day1/Baseline (i.e., Day 2), will be used as baseline if not already performed on the first day of visit Day1/Baseline (i.e., Day 1). If there is more than one value on/before the day of the first dose, the non-missing value closest to and prior to the first dose will be used as the baseline value

Unless stated otherwise, all statistical tests will be 2-sided with statistical significance level of 0.10.

The statistical software, SAS 9.4®, will be used for all summaries and statistical analyses.

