4.5.8 Electrocardiogram (ECG)

The ECG data will be obtained directly from the 12-lead ECG traces. These data include the PR interval, QTcB interval, QTcF interval, QRS duration, and pulse rate. The ECG data will be listed by subject. Descriptive statistics will be used to summarize ECG measurements at each visit for each treatment group. In addition, a shift table of ECG interpretation results will be presented at each visit by treatment group. Individual subject listings of ECG parameters at each timepoint will also be provided by treatment group. Plots of mean QTcB and mean QTcF over time will be also presented.

Visit windows for by visit summaries

For ECG by visit summaries, the analysis visit should be defined using window in the table below. If there is more than 1 value in the same analysis visit window for a certain parameter for a subject, the closest record to the target visit day will be used for the by visit analysis. If there are 2 values in the same analysis visit window with the same distance from the target visit day for a certain parameter for a subject, then the record with the later date will be used for the by visit analysis.

Table 12: Visit windows for ECG

Analysis visit	Target visit day	Analysis visit window
Baseline	1	Most recent non-missing pre-dose value
Week 2	15	[2, 21]
Week 4	29	[22, 35]
Week 6	43	[36, 49]
Week 8	57	[50, 70]
Week 12	85	[71, EOS]

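### The SAP's ECG rules contradict the protocol's triplicate-mean QTc baseline, plan no QTc change or threshold summary, and give the Japan post-dose ECGs no rows of their own

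*SAP*

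**What the plan says.** **Baseline.** Protocol 14.1.6 has the triplicate tracings taken about 2 to 4 minutes apart and makes "the average of the triplet ECG measurements collected before dosing on Day 1" the subject's baseline QTc. Protocol Table 4 schedules that Day 1 triplicate at all sites; later scheduled ECGs are single. SAP 4.1 covers the case of more than one value up to the day of first dose: "the non-missing value closest to and prior to the first dose will be used as the baseline value". SAP Table 12 gives the ECG baseline as "Most recent non-missing pre-dose value". Neither SAP place mentions averaging.

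**Outputs.** SAP 4.5.8 states: "Descriptive statistics will be used to summarize ECG measurements at each visit for each treatment group". By SAP 4.1, for continuous data, "summary statistics will include the arithmetic mean, arithmetic standard deviation (SD), median, minimum (Min), maximum (Max) and n". Section 4.5.8 adds a shift table of ECG interpretation by visit and arm, individual listings at each timepoint, and plots: "Plots of mean QTcB and mean QTcF over time will be also presented".

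**Thresholds.** Protocol 14.1.6 calls for confirmatory ECGs when QTc rises by at least 45 msec from baseline or reaches at least 500 msec, and for further repeats while it stays there.

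**Japan ECGs.** Protocol Table 4, footnote 10, says that on Day 1 at Japanese sites "additional safety evaluations (AE recording, 12-lead ECG, brief neurological examination, and SARA) will be performed 2-hours postdose". The same set of assessments is repeated 2 hours post-dose on Day 8. The first post-baseline row of SAP Table 12 is Week 2, target Day 15, window Days 2 to 21.

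**The concern.** There are three gaps between what the protocol collects and what the SAP reports.

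First, the two documents define baseline QTc differently. A site checking a 45 msec rise works from the mean of three tracings, while an analyst following the SAP works from one. Any QTc change derived under the SAP could then disagree with the change on which the site acted, and it would be noisier than the data require.

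Second, the protocol singles out two QTc limits as needing attention, but the SAP does not say that subjects reaching them will be counted by arm.

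Third, footnote 10 adds ECGs at a fixed time after dosing, and the by-visit tables have no place of their own for them.

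At stake is how clearly the safety report can show whether QTc prolongation differs between arms.

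**Working it through.** The plan gives no figure to reproduce on this point. The check compares texts, adds one piece of noise arithmetic, and maps visit days to windows.

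**1. Baseline.** The Day 1 triplicate supplies three pre-dose values, so the SAP 4.1 rule for more than one value applies. It selects the value closest before the dose, which is the last of the three tracings. Table 12 repeats that rule and makes no exception for ECG.

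Noise in a change from baseline, with *s* the SD of one tracing's reading error, independent errors, and a single post-baseline ECG:

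- Single-tracing baseline: variance s² + s² = 2s², so SD = s√2.
- Triplicate-mean baseline: variance s² + s²/3 = (4/3)s², so SD = s√(4/3).
- Ratio: √2 / √(4/3) = √1.5 = 1.22, for any *s*.

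The documents give no *s*. For a range of assumed values, the chance that reading noise alone gives a rise of at least 45 msec on one ECG is 1 − Φ(45/SD):

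| Assumed s (msec) | SD of change, single / triplicate mean | Chance of at least +45 msec, single / triplicate mean |
|---|---|---|
| 5 | 7.1 / 5.8 | negligible / negligible |
| 8 | 11.3 / 9.2 | 0.003% / 0.00006% |
| 10 | 14.1 / 11.5 | 0.07% / 0.005% |
| 15 | 21.2 / 17.3 | 1.7% / 0.5% |

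**2. Planned outputs by type of safety data.**

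| | Change from baseline | Counts by arm against numeric limits |
|---|---|---|
| Laboratory (SAP 4.5.3) | yes | yes (Table 7 and liver criteria) |
| Vital signs (SAP 4.5.4) | yes | yes (Table 8) |
| ECG (SAP 4.5.8) | not stated | none; shift table of interpretation only |

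The by-visit tables keep one ECG per window. Ties on distance go to the later date. There is no rule for several ECGs on the same day, whereas SAP 4.5.3.1 has one for laboratory values (later time). A prolonged QTc triggers same-day repeats under protocol 14.1.6, so which of those values enters the table is undefined.

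**3. Window mapping (Table 12).**

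- Day 1, 2 hours post-dose: it is not pre-dose, so it is not baseline, and it falls before Day 2, so it is not Week 2. It has no window.
- Day 8 visit: with the protocol's ±3 days it falls on Days 5 to 11, all inside Days 2 to 21, and so maps to Week 2. Its distance from target Day 15 is at least 15 − 11 = 4 days.
- Week 2 visit in window: Days 12 to 18, at most 3 days from target.
- Since 4 > 3, an in-window Week 2 ECG always displaces the Day 8 ECG. If no closer record exists, the Day 8 2-hour post-dose ECG is reported as Week 2.

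Protocol Table 4 attaches the same footnote 10 to the Week 1 brief neurological examination, SARA and ECG. SAP Tables 10 and 11 give the first two a Week 1 row (Days 2 to 10). Table 12 gives ECG none, which looks like an oversight.

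**The case against.** **The averaged value could be entered as the baseline value.** The Table 12 wording is the generic phrase used in the other safety tables, and it does not reject averaging. But SAP 4.1 says what to do when several values exist: take the one nearest the dose. A mean of three tracings does not fit that rule, and nothing in the SAP tells a programmer to derive one.

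**QTc is not reported only as means.** A reader might infer that from the planned plots, but it would be wrong. SD, median, minimum, maximum, the interpretation shift table and the listings are all planned, and ECG findings that the investigator judges clinically significant are recorded as adverse events. What remains is narrower: a maximum per visit is neither a count of subjects nor a change, and an interpretation category is not a QTc limit.

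**No protocol commitment is broken by the missing counts.** This stands. The 45 and 500 msec limits trigger repeat ECGs and monitoring, and protocol 16.4.2 does not list ECG among the data to be evaluated. The counts are a reasonable addition, in line with how the SAP treats laboratory data and vital signs.

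**The noise figures attach to no planned table.** This also stands. Since 4.5.8 states no QTc change and no 45 msec count, a reader should not infer that false exceedances will distort a planned result. The ratio of 1.22 matters once such outputs are added. It describes reading error only; QTc variation between visits affects both definitions and dilutes the gain.

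**The Japan ECGs are not lost.** Both appear in the listings, and the Day 8 ECG feeds the subject-level review in protocol 14.3. Day 8 does have a window, so it would be wrong to say that both ECGs lack one. The number of Japan subjects is not given, so the weight of separate rows is unknown.

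**Conclusion.** The point holds in three limited parts. The baseline definitions contradict each other: the SAP as written uses one tracing and the protocol the mean of three. SAP 4.5.8 states no QTc change-from-baseline summary and no count by arm at the protocol's two limits. In Table 12 the Japan Day 1 post-dose ECG has no window, and the Day 8 ECG is absorbed into Week 2 and normally displaced there.

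The size is modest. The factor of 1.22 assumes independent reading errors. The false-exceedance chances depend on an assumed per-tracing SD and are small under either baseline. The window result needs only the protocol's ±3 days and the closest-to-target rule. The statement about outputs concerns the legible text of 4.5.8; redacted SAP sections are not counted as missing.

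A reader might infer that subjects are monitored less safely. The documents do not support that, because sites follow protocol 14.1.6 whatever the SAP says. Efficacy analyses and sample size are unaffected. The SAP should be corrected, mainly because the change is cheap and the definitions conflict.

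**What to change.** - **Baseline.** In SAP 4.1 and Table 12, define ECG baseline as the mean of the Day 1 pre-dose triplicate, as the protocol does.
- **QTc outputs.** In SAP 4.5.8, add QTcF change from baseline by visit and arm. Add the number and percentage of subjects by arm with QTcF at least 45 msec above baseline and at least 500 msec, using any post-baseline ECG, including unscheduled repeats. That also stops a same-day repeat from hiding the value that triggered it.
- **Windows.** In Table 12, add a Day 1 2-hour post-dose row and a Week 1 row, both marked as Japan sites, and start Week 2 after Week 1, as Tables 10 and 11 do (Week 1 Days 2 to 10, Week 2 from Day 11).

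The cost is SAP wording and a few extra table shells. No new data are needed.

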4.5.9 COVID-19 Related Analyses

Any impacts to the study or study data due to COVID-19 will be summarised and/or listed. These include:

- Participant accountability of participants who discontinued due to COVID-19.
- COVID-19 adverse events.
- Concomitant non-drug treatment related to COVID-19.
- Protocol deviations due to COVID-19.
- Participants with protocol alternations due to COVID-19 (as reported on the COVID-19 Impact Log).

[REDACTED]

[REDACTED]

[REDACTED]

[REDACTED]

[REDACTED]

[REDACTED]

[REDACTED]

[REDACTED]

[REDACTED]

[REDACTED] [REDACTED]

[REDACTED]

[REDACTED] [REDACTED]

[REDACTED]

[REDACTED]

[REDACTED]

5. INTERIM ANALYSIS

An interim analysis (IA) for futility of the primary endpoint will be performed after approximately 50% of the subjects have completed the Week 12 Visit. This is to allow early termination of the study if it is evident that the efficacy of BIIB104 is unlikely to be achieved.

The futility criteria will be based on conditional power, which is the probability that the primary efficacy endpoint analysis will be statistically significant in favour of the treatment at the planned final analysis, given the data at the IA.

The conditional power will be calculated using PROC SEQTEST which allows for calculation under different hypothesised treatment effects and assumed variance. The treatment effects and variance to be used for calculating the conditional power will be determined as follows:

- The treatment effects will be assumed to be equal to the observed values at the IA, *i.e.* the maximum likelihood estimate (MLE).
- Prior to unblinding at the interim analysis, the pooled variance will be assessed to project the likely amount of statistical information at the final analysis. If the pooled variance is less than the value assumed in the study design the pooled variance will be used to calculate the assumed quantity of information at the final analysis. If the pooled variance is greater than the value assumed in the study design the value assumed in the study design will be used to calculate the assumed quantity of information at the final analysis. This approach ensures the futility analysis is conservative for falsely declaring futility.
- For additional context, conditional power under other hypotheses may be calculated.

No test for superiority will be performed at the IA, while the LS mean differences and corresponding standard errors will be derived from the primary analysis model.

The interim analysis results will be reviewed by a Biogen internal unblinded team. Given the insufficient knowledge of BIIB104's potential effects on various cognitive and functional endpoints at this clinical stage, selected analyses on key efficacy endpoints in addition to the pre-specified futility criteria will also be considered for the decision to stop one or both BIIB104 dose arms. Details of these analyses and criteria for futility are documented separately.

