16.6. Sample Size Considerations

Fifty-one subjects per treatment group will have approximately 80% power to detect a true mean difference of 3.5 in change from baseline MCCB Working Memory Domain score to Week 12 between the treatment and placebo groups. With the assumed drop-out rate of 30%, 73 subjects are required from each group to maintain the 80% power. This power calculation is based on a 2-sided *t*-test assuming equal variance with a final significance level of 0.1, and an SD of 7. The statistical software EAST 6.3® is used for sample size calculation. The sample size may be re-estimated based on blinded data review and evolving development of this study.

CONFIDENTIAL

The information contained herein may not be used, disclosed, or published without the written consent of
Biogen MA Inc.

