2. STUDY DESIGN

2.1 Study Overview

This is a Phase 2, randomized, double-blind, placebo-controlled, parallel-group study to evaluate the safety, tolerability, and efficacy of BIIB104 in subjects with CIAS. Approximately 219 male and female subjects with stable schizophrenia from age 18 to 55 years, inclusive, will be recruited. Dosing with BIIB104 0.15 mg BID and 0.5 mg BID versus placebo BID will be evaluated over a treatment phase of 12 weeks. The study will be conducted at approximately 80 sites globally including non-English speaking countries.

The study includes a screening phase, a placebo lead-in phase, a randomized treatment phase, and a safety follow-up (SFU) phase to begin after the last dose of study treatment.

Screening evaluation will occur up to 35 days prior to randomization. Once eligibility has been established, a 7-day Placebo Lead-In evaluation will be conducted to assess the subject's ability to comply with dosing requirements. After Sponsor confirmation of eligibility and completion of baseline measurements at the Baseline/Day 1 Visit, subjects will be randomized in a 1:1:1 ratio to receive BIIB104 0.5 mg, BIIB104 0.15 mg, or placebo. Subjects will be dosed at approximately 12-hour intervals for 12 weeks. Total duration of subject participation will be approximately 19 weeks from screening to final follow-up visit.

[figure not shown]
There are 3 treatment groups and subjects are randomized in a 1:1:1 ratio into 1 of 3 treatment groups. The randomization will be stratified by region.

Table1: Treatment groups

Treatment Groups	Description
Placebo group	Up to 73 subjects to receive oral dosing BID with placebo for 12 weeks.
BIIB104 0.15 mg group	Up to 73 subjects to receive oral dosing BID with BIIB104 0.15 mg for 12 weeks
BIIB104 0.5 mg group	Up to 73 subjects to receive oral dosing BID with BIIB104 0.5 mg for 12 weeks

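### The futility projection may set adjusted interim information against unadjusted final information, so the SAP's assurance against false futility does not hold in general

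*SAP*

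**What the plan says.** SAP section 5 bases futility on conditional power under the observed interim effect. On the interim side, "the LS mean differences and corresponding standard errors will be derived from the primary analysis model". SAP section 4.4.1 defines that model as an MMRM with baseline, baseline-by-visit and region terms and an unstructured covariance, so interim information (1/SE²) is adjusted and also draws on Weeks 2 and 6.

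On the final side, information is projected from a pooled variance assessed before unblinding when that variance is below the design value. When it is above, "the value assumed in the study design will be used to calculate the assumed quantity of information at the final analysis". The only design variance in the documents is in Protocol 16.6 (repeated in SAP section 3), for a two-sample t-test without covariates, "assuming equal variance with a final significance level of 0.1, and an SD of 7".

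The SAP concludes: "This approach ensures the futility analysis is conservative for falsely declaring futility". It does not say whether the pooled variance is raw or model-adjusted, or how many final completers enter the projection. The futility criteria are documented separately.

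**The concern.** Conditional power depends on interim information, final information and the observed effect. The ratio of the two information levels means something only if both are on one scale. Adjusting for baseline reduces the variance of change, so an MMRM standard error carries more information per completer than a raw SD of 7 implies.

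Setting adjusted interim information against unadjusted final information makes the trial look further along than it is and makes the projected final Z too small. When the projected Z is below 1.645, both errors lower conditional power. Taking the smaller of two variances protects against an inflated variance estimate, but not against a change of scale. What is at stake is a recommendation to stop a dose arm whose like-for-like conditional power is above the threshold, which is the error the SAP says its rule rules out.

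**Working it through.** **Design figures.** "Fifty-one subjects per treatment group will have approximately 80% power to detect a true mean difference of 3.5". With SD 7 and n = 51, the noncentrality is 3.5/(7·√(2/51)) = 2.525, and noncentral t power at two-sided 0.10 is 0.806. Then 51/0.7 = 72.9, so 73. Both figures reproduce.

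**Inputs from the documents.** Difference 3.5, SD 7 (variance 49), critical value 1.645, 51 completers or 73 randomised per arm, 1:1:1 allocation, look at about 50%. The base of the 50% is not stated: half of 51 is 25.5 per arm, and half of 219 over three arms is 36.5.

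**Assumptions.**
- Baseline to Week 12 correlation r = 0.70 to 0.85, with equal variances and exchangeable visits.
- Conditional power threshold 20%.
- Either no partial follow-up at the look, or 18 subjects per arm with early visits only (9 with Weeks 2 and 6, 9 with Week 2).

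**Formulas.**
- Adjusted variance: Vadj = V·(1+r)/2
- Interim information without partial data: I1 = n1/(2·Vadj)
- Like-for-like final information: I2 = 51/(2·Vadj)
- Mixed final information: I2 = 51/(2·min(V, 49))
- CP = Φ[(θ·√I2 − 1.645)/√(1 − I1/I2)]

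**One case in full** (SD 7, r = 0.70, 25.5 completers, no partial data).
- Vadj = 49 × 0.85 = 41.65, so I1 = 25.5/83.3 = 0.306.
- Like-for-like I2 = 51/83.3 = 0.612, information fraction 0.50.
- Mixed I2 = 51/98 = 0.520, information fraction 0.59.
- Like-for-like CP is 20% at θ = (1.645 − 0.842·√0.5)/√0.612 = 1.342.
- Mixed CP at that θ is Φ[(1.342 × 0.721 − 1.645)/√0.412] = Φ(−1.055) = 14.6%.
- Under the mixed rule the 20% cut moves up to 1.532. At a true 3.5, the chance of falling below the cut goes from Φ[(1.342 − 3.5)·√0.306] = 11.6% to Φ[(1.532 − 3.5)·√0.306] = 13.8%.

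**All cases, SD 7, 51 projected.** With partial data, I1 comes from the known-covariance likelihood, with baseline-adjusted visits correlated r/(1+r).

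| Completers per arm | r | Partial data | Fraction, like-for-like / mixed | 20% reads as | False stopping |
|---|---|---|---|---|---|
| 25.5 | 0.70 | none | 0.50 / 0.59 | 14.6% | 11.6% → 13.8% |
| 25.5 | 0.85 | none | 0.50 / 0.54 | 17.4% | 13.3% → 14.3% |
| 25.5 | 0.70 | 18 | 0.55 / 0.65 | 13.8% | 11.0% → 13.4% |
| 25.5 | 0.85 | 18 | 0.56 / 0.61 | 17.0% | 12.5% → 13.7% |
| 36.5 | 0.70 | none | 0.72 / 0.84 | 8.6% | 9.6% → 13.3% |
| 36.5 | 0.85 | none | 0.72 / 0.77 | 14.9% | 11.3% → 13.0% |
| 36.5 | 0.70 | 18 | 0.77 / 0.91 | 5.2% | 9.5% → 13.9% |
| 36.5 | 0.85 | 18 | 0.78 / 0.85 | 13.1% | 11.2% → 13.3% |

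**Where the direction changes.** The understatement needs the adjusted SD to be below min(raw pooled SD, 7). That covers every raw pooled SD at or below 7 when r < 1. Above 7 it persists up to 7/√((1+r)/2), which is 7.59 at r = 0.70 and 7.28 at r = 0.85. Two checks without partial data:
- Raw pooled SD 8, 51 projected: 20% reads as 23 to 26% (25.5 completers) or 26 to 30% (36.5).
- SD 7, 73 projected when 51 finish: 20% reads as 26 to 29% or 31 to 35%.

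**The case against.** The strongest reply is that the SAP leaves the pooled variance undefined. A residual variance from the primary model fitted without treatment can be computed blinded and fits the text. On that reading both branches work as claimed: the design value replaces the residual variance only when the residual variance exceeds 49, which projects more final information than like-for-like and raises low conditional power. A reader might infer that the design-value fallback breaks the claim even then. It does not.

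A reader might also infer that the rule is shown to favour false futility. The documents do not support that. With a raw pooled SD well above 7, the cap makes the rule conservative, and that is the case it was written for. Projecting 73 per arm also more than offsets the mismatch at SD 7 if 30% drop out, though only by overcounting completers.

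Nor does a low conditional power stop an arm by itself. The threshold is held elsewhere, conditional power under other hypotheses may be calculated, and other key efficacy analyses inform the decision.

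All of this limits the point without removing it. The only benchmark the SAP gives for the pooled variance is an unadjusted one, so the raw reading is the natural one. An assurance that depends on an unstated definition, an unstated final n and the variance that happens to be observed is not secured by the rule as written.

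**Conclusion.** The point stands in conditional form. If the pooled variance is the raw variance of change and about 51 completers per arm are projected, the rule understates conditional power in the futility zone for every raw pooled SD at or below 7, and somewhat above. At SD 7, r of 0.70 to 0.85 and an assumed 20% threshold, 20% reads as about 14 to 17% with 25.5 completers per arm at the look, or 5 to 15% with 36.5. False stopping at a true 3.5 points rises by roughly 1 to 5 percentage points. The size is modest at a half-way look with high correlation, and larger when 36.5 of an eventual 51 have completed.

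The correlation, threshold, partial follow-up and final n are assumptions, because the documents give none of them for this calculation. The effect on an actual stopping decision therefore cannot be quantified from the documents. What can be said is that the claimed protection does not hold in general.

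**What to change.** Before the look, amend SAP section 5 to put both information levels on the MMRM scale, in one of two ways:
- Multiply the interim MMRM information by expected final Week 12 completers divided by interim Week 12 completers. If partial follow-up is a larger share at the look than at the end, this projects slightly too much information, which errs towards continuing.
- Use the blinded residual variance of the primary MMRM fitted without treatment.

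State the final number of completers used. Apply the smaller-variance rule only on that scale. Replace the assurance with the conditions under which the rule is conservative. If these definitions already stand in the separate futility document, the SAP should cite them.

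The cost is a wording change and a few lines of code, with no extra data and no further unblinding. The downside is that futility may be declared slightly less often.
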